6.10.2. Urine Samples

Urine samples will be collected at all study visits, unless otherwise noted for the below noted laboratory analyses:

- Urinalysis

- Urine pregnancy testing for females of childbearing potential only (not collected at Screening and 30 Day-Follow-up Visit). Positive urine pregnancy tests will be confirmed with a serum test. If the serum test is positive, the subject will be discontinued.
- Markers of renal dysfunction (collected fasted): If the subject has not fasted prior to the visit, the visit may proceed, but the subject must return within 72 hours in a fasted state to provide a urine sample for markers of renal dysfunction at Day 1 Visit, Weeks 24, 48, 96 and ESDD (if applicable).

6.10.3. Blood Storage Samples

Any residual blood samples from the samples collected will be frozen and stored. These stored blood samples may be used by the Sponsor or its research partners for HIV-1 and/or HBV or related diseases, genotyping/phenotyping assays or their development, for retesting the amount of HIV-1 and/or HBV in the blood, for measurement of antiviral drug levels in the blood, or for testing to learn more about how the study drug has worked against HIV-1 and/or HBV or related diseases, or clinical laboratory testing to provide additional safety data. No human genetic testing will be performed without expressed consent of study subjects. At the conclusion of this study, these samples may be retained in storage by Gilead Sciences for a period up to 15 years.

6.11. Assessments for Premature Discontinuation from Study

If a subject discontinues study drug in the blinded phase of the study (for example, as a result of an AE), every attempt should be made to keep the subject in the study, and continue to perform the required study procedures until the End of Blinded Treatment Visit. If this is not possible or acceptable to the subject or investigator, the subject may be withdrawn from the study.

6.12. End of Study

End of study is defined as completion of the 96 weeks of treatment and the 30 Day Follow-Up visit. Subjects that enter the extension phase will complete study visits every 12 weeks until the product becomes accessible to subjects through an access program, or until Gilead Sciences elects to discontinue the study in that country, whichever occurs first.

6.13. Post Study Care

After a subject has completed/terminated their participation in the study, long-term care for the subject will remain the responsibility of their primary treating physician.

6.14. HIV-1 Virologic Failure

HIV-1 virologic failure is defined as confirmed virologic rebound or HIV-1 RNA ≥ 50 copies/mL at study drug discontinuation, Week 48, or 96.

6.14.1. Management of HIV-1 Virologic Rebound

Subjects who meet the criteria listed below will be considered to have HIV-1 virologic rebound:

- At any visit, after achieving HIV-1 RNA < 50 copies/mL, a rebound in HIV-1 RNA \geq 50 copies/mL, which is subsequently confirmed at the following scheduled or unscheduled visit; OR
- At any visit, a $> 1 \log_{10}$ increase in HIV-1 RNA from the nadir which is subsequently confirmed at the following scheduled or unscheduled visit

At any visit after achieving HIV-1 RNA < 50 copies/mL, if the HIV-1 RNA is \geq 50 and < 200 copies/mL, a reflex HIV-1 RNA repeat test will be conducted on stored plasma if available. If the repeat result is < 50 copies/mL, no further action is required. If the repeat result is \geq 50 copies/mL subjects will be asked to return to the clinic for a scheduled or unscheduled blood draw (2 to 3 weeks after the date of the original test that resulted in HIV-1 RNA virologic rebound) for confirmation of virologic rebound. If virologic rebound is confirmed at the scheduled or unscheduled visit and the HIV-1 RNA is \geq 200 copies/mL, the blood sample from the confirmation visit will be the primary sample used for HIV-1 genotypic and phenotypic testing.

All subjects with post-baseline resistance analyses will also be analyzed for their HIV-1 RT, PR, and IN genotypes and phenotypes from stored baseline samples. After a subject's first post-baseline resistance test, additional testing will be conducted on a case-by-case basis. Any subject may be discontinued at Investigator's discretion or per local treatment guidelines.

[figure not shown]
If no HIV-1 resistance is detected from the genotype or phenotype, the subject may remain on study drugs and a repeat HIV-1 RNA should be performed (2 to 3 weeks after date of test with HIV-1 RNA \geq 50 copies/mL). Investigators should carefully evaluate the benefits and risks of remaining on study drug for each individual subject and document this assessment in the on-site medical record.

Subjects who are noncompliant on an ongoing basis will be considered for discontinuation per the Investigator's discretion or local treatment guidelines. Investigators who opt to discontinue study drugs for an individual subject must discuss with the Medical Monitor prior to study drug discontinuation.

For subjects who are off study drug but remain on study, it will be the Investigator's discretion to manage virologic rebound.

Please refer to [Figure 6-1](#) for the management of subjects who meet the criteria for virologic rebound.

Figure 6-1. Virologic Rebound Schema

- a If virologic rebound is not confirmed, the subject will remain on their current regimen.
- b If virologic rebound is confirmed and the HIV-1 RNA is ≥ 200 copies/mL, the HIV-1 genotype and phenotype (reverse transcriptase, protease, and integrase) will be analyzed.
- c Based on the results of the genotypic and phenotypic assays, the subject will remain on study drugs or study drugs will be discontinued. If genotyping or phenotyping assay fails, a new ARV regimen may be configured at the discretion of the Investigator.
- d If no resistance is detected, HIV-1 RNA will be repeated (2-3 weeks later). Investigator reviews study drug continuation/discontinuation options and discusses with the Medical Monitor prior to study drug discontinuation
- e A new ARV regimen will be configured, at the Investigator's discretion, and the subject will remain in the study.

6.14.2. Subjects with HIV-1 RNA ≥ 50 copies/mL at Study Discontinuation, Week 48 or 96

Subjects with HIV-1 RNA ≥ 50 copies/mL at study discontinuation (at or after Week 8) or last visit will be considered virologic failures. However, if the HIV-1 RNA is ≥ 50 and < 200 copies/mL, a reflex HIV-1 RNA repeat test will be conducted on stored plasma if available. If the repeat result is < 50 copies/mL, the subject will not be considered a virologic failure.

Subjects with HIV-1 RNA ≥ 50 copies/mL at Week 48 and/or Week 96 will be asked to return for an unscheduled visit within the visit window for a retest. If the HIV-1 RNA is ≥ 50 and < 200 copies/mL, a reflex HIV-1 RNA repeat test will be conducted on stored plasma if available. If the repeat result is < 50 copies/mL, the subject will not be considered a virologic failure and no further action is needed.

Subjects with HIV-1 RNA ≥ 200 copies/mL at study drug discontinuation, last visit, Week 48, and/or Week 96 will also have resistance testing conducted.

6.15. HBV Resistance Surveillance

Sequencing analysis of the HBV pol/RT will be attempted for all subjects who remain viremic (HBV DNA ≥ 69 IU/mL) at Weeks 48 and 96 (or Early Study Drug Discontinuation Visit as early as Week 8), and for those with virologic breakthrough defined as:

- Two consecutive HBV DNA values ≥ 69 IU/mL after achieving < 69 IU/mL, or
- Two consecutive ≥ 1.0 Log₁₀ increases in HBV DNA from nadir for those who did not achieve a result < 69 IU/mL

Sequencing of the corresponding Day 1 sample will also be conducted for any subject who remains viremic or experiences virologic breakthrough. As it may not be known at the time of the visit whether a patient is viremic or if it will be their last study visit, a separate virology sample for potential resistance surveillance will be collected at each study visit. Phenotypic analysis will be performed for adherent subjects that are subjected to sequence analysis.

7. ADVERSE EVENTS AND TOXICITY MANAGEMENT

7.1. Definitions of Adverse Events, Adverse Reactions, and Serious Adverse Events

7.1.1. Adverse Events

An adverse event (AE) is any untoward medical occurrence in a clinical study subject administered a medicinal product, which does not necessarily have a causal relationship with the treatment. An AE can therefore be any unfavorable and/or unintended sign, symptom, or disease temporally associated with the use of a medicinal product, whether or not considered related to the medicinal product. AEs may also include pre- or post-treatment complications that occur as a result of protocol specified procedures, overdose, drug abuse/misuse reports, or occupational exposure. Preexisting events that increase in severity or change in nature during or as a consequence of participation in the clinical study will also be considered AEs.

An AE does not include the following:

- Medical or surgical procedures such as surgery, endoscopy, tooth extraction, and transfusion. The condition that led to the procedure may be an adverse event and must be reported.
- Pre-existing diseases, conditions, or laboratory abnormalities present or detected before the screening visit that do not worsen
- Situations where an untoward medical occurrence has not occurred (e.g. hospitalization for elective surgery, social and/or convenience admissions)
- Overdose without clinical sequelae (see Section 7.6.1)
- Any medical condition or clinically significant laboratory abnormality with an onset date before the consent form is signed and not related to a protocol-associated procedure is not an AE. It is considered to be pre-existing and should be documented on the medical history eCRF.

7.1.2. Serious Adverse Events

A **serious adverse event** (SAE) is defined as an event that, at any dose, results in the following:

- Death
- Life-threatening (Note: The term “life-threatening” in the definition of “serious” refers to an event in which the subject was at risk of death at the time of the event; it does not refer to an event that hypothetically might have caused death if it were more severe.)
- In-patient hospitalization or prolongation of existing hospitalization
- Persistent or significant disability/incapacity

- A congenital anomaly/birth defect
- A medically important event or reaction: such events may not be immediately life-threatening or result in death or hospitalization but may jeopardize the subject or may require intervention to prevent one of the other outcomes constituting SAEs. Medical and scientific judgment must be exercised to determine whether such an event is a reportable under expedited reporting rules. Examples of medically important events include intensive treatment in an emergency room or at home for allergic bronchospasm; blood dyscrasias or convulsions that do not result in hospitalization; and development of drug dependency or drug abuse. For the avoidance of doubt, infections resulting from contaminated medicinal product will be considered a medically important event and subject to expedited reporting requirements.

7.1.3. Clinical Laboratory Abnormalities and Other Abnormal Assessments as Adverse Events or Serious Adverse Events

Laboratory abnormalities without clinical significance are not recorded as AEs or SAEs. However, laboratory abnormalities (eg, clinical chemistry, hematology, and urinalysis) that require medical or surgical intervention or lead to IMP interruption, modification, or discontinuation must be recorded as an AE, as well as an SAE, if applicable. In addition, laboratory or other abnormal assessments (eg, electrocardiogram, x-rays, vital signs) that are associated with signs and/or symptoms must be recorded as an AE or SAE if they meet the definition of an AE or SAE as described in Sections 7.1.1 and 7.1.2. If the laboratory abnormality is part of a syndrome, record the syndrome or diagnosis (eg, anemia), not the laboratory result (ie, decreased hemoglobin).

For specific information on handling of clinical laboratory abnormalities in this study, please refer to Section 7.5.

7.2. Assessment of Adverse Events and Serious Adverse Events

The investigator or qualified subinvestigator is responsible for assessing AEs and SAEs for causality and severity, and for final review and confirmation of accuracy of event information and assessments.

7.2.1. Assessment of Causality for Study Drugs and Procedures

The investigator or qualified subinvestigator is responsible for assessing the relationship to IMP therapy using clinical judgment and the following considerations:

- **No:** Evidence exists that the adverse event has an etiology other than the IMP. For SAEs, an alternative causality must be provided (e.g., pre-existing condition, underlying disease, intercurrent illness, or concomitant medication).
- **Yes:** There is reasonable possibility that the event may have been caused by the investigational medicinal product.

It should be emphasized that ineffective treatment should not be considered as causally related in the context of adverse event reporting.

The relationship to study procedures (e.g., invasive procedures such as venipuncture or biopsy) should be assessed using the following considerations:

- **No:** Evidence exists that the adverse event has an etiology other than the study procedure.
- **Yes:** The adverse event occurred as a result of protocol procedures, (eg, venipuncture)

7.2.2. Assessment of Severity

7.3. Investigator Requirements and Instructions for Reporting Adverse Events and Serious Adverse Events to Gilead

Requirements for collection prior to study drug initiation:

After informed consent, but prior to initiation of study medication, the following types of events should be reported on the case report form (eCRF): all SAEs and adverse events related to protocol-mandated procedures.

Adverse Events

Following initiation of study medication, collect all AEs, regardless of cause or relationship, until 30-days after last administration of study IMP must be reported to the eCRF database as instructed.

All AEs should be followed up until resolution or until the adverse event is stable, if possible. Gilead Sciences may request that certain AEs be followed beyond the protocol defined follow up period.

Serious Adverse Events

All SAEs, regardless of cause or relationship, that occurs after the subject first consents to participate in the study (ie, signing the informed consent) and throughout the duration of the study, including the protocol-required post treatment follow-up period, must be reported to the eCRF database and Gilead Pharmacovigilance and Epidemiology (PVE) as instructed. This also includes any SAEs resulting from protocol-associated procedures performed after informed consent is signed.

Any SAEs and deaths that occur after the post treatment follow-up visit but within 30-days of the last dose of study IMP, regardless of causality, should also be reported.

Investigators are not obligated to actively seek SAEs after the protocol defined follow up period - however, if the investigator learns of any SAEs that occur after study participation has concluded and the event is deemed relevant to the use of IMP, he/she should promptly document and report the event to Gilead PVE.

- All AEs and SAEs will be recorded in the eCRF database within the timelines outlined in the eCRF completion guideline.

All investigators will receive a safety letter notifying them of relevant SUSAR reports associated with any study IMP. The investigator should notify the IRB or IEC of SUSAR reports as soon as is practical, where this is required by local regulatory agencies, and in accordance with the local institutional policy.

7.5. Toxicity Management

All clinical and clinically significant laboratory toxicities will be managed according to uniform guidelines detailed in [Appendix 4](#) and as outlined below.

- Clinical events and clinically significant laboratory abnormalities will be graded according to the GSI Grading Scale for Severity of Adverse Events and Laboratory Abnormalities ([Appendix 5](#)).
- Grade 3 and 4 clinically significant laboratory abnormalities should be confirmed by repeat testing within 3 calendar days of receipt of results and before investigational medicinal product discontinuation, unless such a delay is not consistent with good medical practice
- Any questions regarding toxicity management should be directed to the Gilead Medical Monitor.

7.5.1. Grades 1 and 2 Laboratory Abnormality or Clinical Event

Continue study drug at the discretion of the Investigator.

7.5.2. Grade 3 Laboratory Abnormality or Clinical Event

- For Grade 3 clinically significant laboratory abnormality or clinical event, investigational medicinal product may be continued if the event is considered to be unrelated to investigational medicinal product.
- For a Grade 3 clinical event, or clinically significant laboratory abnormality confirmed by repeat testing, that is considered to be related to investigational medicinal product, investigational medicinal product will be withheld until the toxicity returns to Grade 2. When restarting investigational medicinal product following resolution of the adverse event, the investigational medicinal product should be restarted at full dose upon discussion with the Gilead Sciences Medical Monitor.
- If a laboratory abnormality recurs to \geq Grade 3 following rechallenge with investigational medicinal product and is considered related to investigational medicinal product, then investigational medicinal product will be permanently discontinued and the subject managed according to local practice. Recurrence of laboratory abnormalities considered unrelated to investigational medicinal product may not require permanent discontinuation but requires discussion with the Gilead Sciences Medical Monitor.

7.5.3. Grade 4 Laboratory Abnormality or Clinical Event

- For a Grade 4 clinical event or clinically significant Grade 4 laboratory abnormality confirmed by repeat testing that is considered related to investigational medicinal product, investigational medicinal product will be permanently discontinued and the subject managed according to local practice. The subject should be followed as clinically indicated until the laboratory abnormality returns to baseline or is otherwise explained, whichever occurs first. A clinically significant Grade 4 laboratory abnormality that is not confirmed by repeat testing should be managed according to the algorithm for the new toxicity grade.
- Investigational medicinal product may be continued without dose interruption for a clinically non-significant Grade 4 laboratory abnormality (eg, Grade 4 CK after strenuous exercise, or triglyceride elevation that is nonfasting or that can be medically managed) or a clinical event considered unrelated to investigational medicinal product requires discussion with the Gilead Sciences Medical Monitor.

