7.5.4. On-Treatment ALT Flare and Post-Treatment Exacerbation of Hepatitis B Management

In On-Treatment ALT Flare is defined as:

- Confirmed (within 3 days of receipt of initial laboratory results) serum ALT $> 2 \times$ Day 1 value and $>10 \times$ ULN, with or without associated symptoms.

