7.5.4.1. Management of ALT Flare in Subjects Receiving Study Medication

If laboratory results indicate elevation of ALT $> 2 \times$ Day 1 value and $> 10 \times$ ULN, the following is recommended:

- Schedule the subject to return to the clinic as soon as possible (ideally within 3 days after initial laboratory results were drawn). During the visit, a clinical assessment of the subject will be performed. The assessment should include a physical examination and evaluation of the subject's mental status.
- If the ALT elevation is confirmed, request the central clinical laboratory to conduct reflex testing for PT/INR, plasma HBV DNA, HBV serology (HBsAg, HBsAb, HBeAg and HBeAb), HDV, HAV IgM, and HCV serology
- Check the following laboratory parameters: serum ALT and AST, total bilirubin, INR, and serum albumin. Based on the results of the confirmatory tests, the following treatment modifications are recommended.

Elevated Liver Enzymes, Normal or Stable relative to Day 1 Liver Function Tests

If ALT levels are elevated (ie, $> 2 \times$ Day 1 and $> 10 \times$ ULN) with normal or stable total bilirubin and INR relative to Day 1, the subject may remain on study medication and should be monitored weekly as long as ALT levels return to normal or Day 1 level. During monitoring, if the ALT values remain persistently elevated, the Investigator should discuss with the Gilead Medical Monitor whether the study drug should be discontinued.

Elevated Liver Enzymes, Elevated Liver Function Tests

If ALT values are elevated (ie, $> 2 \times$ Day 1 and $> 10 \times$ ULN), and total bilirubin is confirmed to be 2 x Day 1 value, and INR is 0.5 above Day 1, provided both are $> ULN$, the investigator should consider discontinuing study medication (upon discussion with the Gilead Medical Monitor, unless the safety of the patient is of immediate concern). The subject should be monitored weekly as long as ALT, total bilirubin, and INR values remain elevated or above Day 1 values.

During monitoring, if the ALT values and the liver function tests remain persistently elevated, the Investigator should discuss with the Gilead Medical Monitor whether the study drug should be discontinued.

7.5.4.2. Management of Exacerbation of Hepatitis B in Subjects who have Discontinued Study Medication

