ALT (SGPT)	1.25 to 2.50 × ULN	> 2.50 to 5.00 × ULN	> 5.00 to 10.00 × ULN	> 10.00 × ULN
GGT	1.25 to 2.50 × ULN	> 2.50 to 5.00 × ULN	> 5.00 to 10.00 × ULN	> 10.00 × ULN
Alkaline Phosphatase	1.25 to 2.50 × ULN	> 2.50 to 5.00 × ULN	> 5.00 to 10.00 × ULN	> 10.00 × ULN
Total Amylase	> 1.0 to 1.5 × ULN	> 1.5 to 2.0 × ULN	> 2.0 to 5.0 × ULN	> 5.0 × ULN
Pancreatic Amylase	> 1.0 to 1.5 × ULN	> 1.5 to 2.0 × ULN	> 2.0 to 5.0 × ULN	> 5.0 × ULN
Lipase	> 1.0 to 1.5 × ULN	> 1.5 to 3.0 × ULN	> 3.0 to 5.0 × ULN	> 5.0 × ULN
Albumin Pediatrics <16 years	-	2.0 to < LLN g/dL 20 to < LLN g/L	< 2.0 g/dL < 20 g/L	NA
≥ 16 years	3.0 g/dL to < LLN 30 g/L to < LLN	2.0 to < 3.0 g/dL 20 to < 30 g/L	< 2.0 g/dL < 20 g/L	NA

URINALYSIS				
	Grade 1	Grade 2	Grade 3	Grade 4
Hematuria (Dipstick)	1+	2+	3-4+	NA
Hematuria (Quantitative) See Note below				
Females	>ULN - 10 RBC/HPF	> 10-75 RBC/HPF	> 75 RBC/HPF	NA
Males	6-10 RBC/HPF	> 10-75 RBC/HPF	> 75 RBC/HPF	NA
Proteinuria (Dipstick)	1+	2-3+	4+	NA
Proteinuria, 24 Hour Collection				
Adult and Pediatric ≥ 10 Years	200 to 999 mg/24 h	>999 to 1999 mg/24 h	>1999 to 3500 mg/24 h	> 3500 mg/24 h
Pediatric > 3 Mo to < 10 Years	201 to 499 mg/m ² /24 h	>499 to 799 mg/m ² /24 h	>799 to 1000 mg/m ² /24 h	> 1000 mg/ m ² /24 h
Glycosuria (Dipstick)	1+	2-3+	4+	NA

Notes:

- Toxicity grades for Quantitative and Dipstick Hematuria will be assigned by Covance Laboratory, however for other laboratories, toxicity grades will only be assigned to Dipstick Hematuria.
- With the exception of lipid tests, any graded laboratory test with a result that is between the LLN and ULN should be assigned Grade 0.
- If the severity of a clinical AE could fall under either one of two grades (e.g. the severity of an AE could be either Grade 2 or Grade 3), select the higher of the two grades for the AE.

CARDIOVASCULAR				
	Grade 1	Grade 2	Grade 3	Grade 4
Cardiac Arrhythmia (general) (By ECG or physical exam)	Asymptomatic AND No intervention indicated	Asymptomatic AND Non-urgent medical intervention indicated	Symptomatic, non-life-threatening AND Non-urgent medical intervention indicated	Life-threatening arrhythmia OR Urgent intervention indicated
Cardiac-ischemia/Infarction	NA	NA	Symptomatic ischemia (stable angina) OR Testing consistent with ischemia	Unstable angina OR Acute myocardial infarction

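### For a confirmed ALT flare judged related and clinically significant, Protocol 7.5.3 requires permanent discontinuation while 7.5.4.1 allows continuation, and no readable text says which governs

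*Protocol*

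**What the plan says.** Protocol Section 7.5 manages toxicities through Appendix 4 and through the subsections that follow it. Three pieces of text bear on a high ALT.

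- **Section 7.5.3** covers a "clinically significant Grade 4 laboratory abnormality confirmed by repeat testing". If the abnormality is "considered related to investigational medicinal product, investigational medicinal product will be permanently discontinued". The section lets drug continue for Grade 4 results that are not clinically significant, and its examples are creatine kinase after exercise and triglycerides. It does not mention ALT or flares.
- **Appendix 5** gives the ALT grades, from 1 to 4, as "ALT (SGPT) 1.25 to 2.50 × ULN > 2.50 to 5.00 × ULN > 5.00 to 10.00 × ULN > 10.00 × ULN".
- **Sections 7.5.4 and 7.5.4.1** define a flare as "Confirmed (within 3 days of receipt of initial laboratory results) serum ALT" above 2 × the Day 1 value and above 10 × ULN, with or without symptoms. Causality is not part of the definition. Where bilirubin and INR, compared with Day 1, are normal or stable, the section reads: "the subject may remain on study medication and should be monitored weekly as long as ALT levels return to normal or Day 1 level". With lasting elevation, "if the ALT values remain persistently elevated, the Investigator should discuss with the Gilead Medical Monitor whether the study drug should be discontinued". If bilirubin and INR have also risen by the stated amounts, "the investigator should consider discontinuing study medication".

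Neither 7.5.3 nor 7.5.4.1 refers to the other.

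**The concern.** A flare uses the same multiple of ULN as Grade 4 ALT, so one laboratory result can fall under both sections. One section makes permanent discontinuation mandatory once its conditions are met. The other leaves the decision open in both of its branches and does not exclude related events. Two sites following the text in good faith could reach opposite decisions.

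The stakes are mainly clinical. All participants have hepatitis B, Section 1.6 describes flares as fairly common early in treatment, and 7.5.4.2 exists because hepatitis B can worsen after drug is stopped. There is also a smaller route to the primary endpoint, because stopping drug for an adverse event can make a participant a non-responder in the HIV snapshot.

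**Working it through.** No power or alpha figure is involved. The check compares conditions, then looks for a precedence rule, then bounds the endpoint effect.

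**1. Thresholds.** Write the ALT value and the Day 1 value D in multiples of ULN.

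- Grade 4 (Appendix 5): ALT > 10.
- Flare (7.5.4): ALT > max(10, 2D), confirmed.

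Since max(10, 2D) ≥ 10, every flare is a Grade 4 ALT. Both are confirmed by repeat testing: 7.5 asks for this within 3 calendar days of receiving a Grade 3 or 4 result, and 7.5.4 sets 3 days for a flare.

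**2. The converse.** The thresholds coincide only when 2D ≤ 10, that is D ≤ 5. Inclusion criterion 7 allows ALT up to 10 × ULN, so D > 5 is possible. With D = 8, 2D = 16: a value above 10 and up to 16 × ULN is Grade 4 but not a flare, and only 7.5.3 applies.

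**3. Actions for a confirmed flare.**

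| Flare judged | 7.5.3 | 7.5.4.1, bilirubin and INR stable | 7.5.4.1, both raised |
|---|---|---|---|
| Unrelated, or not clinically significant | No mandatory stop | May continue | Consider stopping |
| Related and clinically significant | Permanent stop | May continue | Consider stopping |

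The texts diverge only in the second row, in both branches of 7.5.4.1.

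**4. Search for a precedence rule.**

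- The opening of 7.5 covers all its subsections without ranking them.
- Section 1.6 refers flares to 7.5.4 for monitoring but does not say that 7.5.4 displaces 7.5.3.
- Section 6.9 (criteria for stopping treatment) does not address the question.
- SAP 7.2.5 defines ALT elevation for analysis only.
- Appendix 4, which 7.5 cites, appears in the text available to us only as a heading. Its content could not be checked.

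**5. Endpoint effect.** Under Section 8.5.1.1 the Week 48 window is Days 295 to 378, and HIV-1 RNA counts up to 1 day after the last dose. A participant who stops for an adverse event is a non-response only if there is no on-treatment value in that window. A last dose on or before Day 293 guarantees this, since 293 + 1 = 294 < 295. If the participant would otherwise have responded, the arm's rate falls by 1/120 = 0.0083, or 0.83 percentage points. A stop after an in-window value below 50 copies/mL remains a response, and a stop after Day 378 has no Week 48 effect.

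**The case against.** The best defence is that the two texts can both be followed. A permission and a conditional requirement are compatible if 7.5.4.1 is read as covering flares in general and 7.5.3 as removing the related, clinically significant ones. In addition, 7.5.4.1 orders a work-up for viral causes, so many flares may be attributed to underlying disease and never meet 7.5.3. Section 1.6 points to 7.5.4 by number. Questions about toxicity go to the medical monitor, who would often see both cases.

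Much of this stands. It narrows the conflict to the related, clinically significant subset and makes discordant handling less likely. It does not remove the conflict. That the requirement prevails over the permission is an inference, and so is the opposite view that the specific section prevails over the general one. The protocol states neither. The pointer in Section 1.6 is also loose: it describes a flare as a five-fold ALT rise above the upper limit, whereas 7.5.4 uses 10 × ULN.

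A reader might also infer three stronger claims, which the documents do not support:

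- **That the two rules overlap completely.** Flares are a subset of Grade 4 ALT, and a strict one when Day 1 ALT exceeds 5 × ULN.
- **That the protocol nowhere settles precedence.** Appendix 4 could not be read, so this holds only for the readable text.
- **That each discordant decision shifts an arm by 0.83 points, or biases the comparison.** The figure is a ceiling per participant. Treatment is double-blind, and nothing in the documents suggests that handling would differ by arm.

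**Conclusion.** The inconsistency is real and limited. It applies to confirmed on-treatment flares that the investigator judges both related and clinically significant. For these, 7.5.3 mandates a permanent stop and 7.5.4.1 does not. The conclusion that precedence is unstated rests on the readable text and would need revisiting if Appendix 4 contains such a rule.

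The case for acting is consistent handling of patient safety. The documents give no frequency for such flares, so no total effect on the Week 48 response rate can be stated; only the per-participant maximum of 0.83 points is supported, assuming 120 participants per arm. Nothing here implies that either clinical rule is the correct one.

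**What to change.** Reconcile Sections 7.5.3 and 7.5.4.1 with Appendix 4, and state in each which governs when an ALT flare is also a related, clinically significant Grade 4 abnormality. Cross-refer the sections.

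In the same edit, reconcile the two weekly-monitoring conditions in 7.5.4.1. The first branch ties monitoring to ALT returning to normal or to the Day 1 level; the second ties it to ALT, bilirubin and INR staying elevated. As written they point in opposite directions.

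The choice of clinical rule belongs to the sponsor. The cost is protocol wording and notice to sites; sample size, endpoints and analysis methods are unaffected.
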